7.1 Analysis Periods

Analysis periods are defined as follows:

- Pre-treatment period: Begins at the first screening visit and ends on the start date of study therapy (DCV or SOF).
- On-treatment period: Begins after the start date of study therapy and ends on the last date of study therapy plus 7 days. The 7-day cut-off reflects the point at which minimal antiviral activity related to study therapy is present. It is also expected that minimal drug exposure and undetectable drug levels will be present beyond 7 days post-dose.
- Follow-up period: Begins after the last date of study therapy plus 7 days.

Refer to Section 5.1 for slotting Day 1 measurements according to domain.

7.2 Analysis Windows and Multiple Records

Analysis visit windows are defined within analysis periods as follows:

- Select values in the appropriate analysis period.
- Slot observations into analysis visit windows (e.g., "WK 4", "F/U WK 12") defined in Table 7.2-1. Analysis visit windows are generally defined according to mid-points between visits.

Table 7.2-1: Analysis Windows

Abbreviated Analysis Visit Label in Output	Target Visit Day in Analysis Period	Study Days in Analysis Period
PRE-TRT		

Table 7.2-1: Analysis Windows

Abbreviated Analysis Visit Label in Output	Target Visit Day in Analysis Period	Study Days in Analysis Period				
B/L ^a	1	≤1				
ON-TRT						
UNS	4	[2, 6]				
DAY 10	10	[7, 13]				
WK 4	28	[14, 42]				
WK 8	56	[43, 70]				
WK 12	84	[71, 98]				
WK 16	42	> 98				
F/U^{b}						
F/U WK 4	21	[7, 49]				
F/U WK 12	77	[50, 119]				
F/U WK 24	161	[120, 245]				
F/U WK 48	329	[246, 413]				
F/U WK 72	497	[414, 581]				
F/U WK 96	665	[582, 707]				
F/U WK 108	749	[708, 791]				
F/U WK 120	833	> 791				

^a Baseline in longitudinal summaries

For longitudinal analyses within an analysis window, then select one value for analyses as follows:

- HCV RNA on treatment: Closest value collected relative to the target visit day (as determined
 by the absolute difference in days between the target visit day and the collection day, and the
 absolute difference in days between the target visit day and the assay day); if there are ties,
 then select first value assayed.
- HCV RNA during follow-up: Last value collected; if there are ties, then select first value assayed.
- Other: Last value measured or collected; if there are ties, then select last entered. For questionnaires with multiple items, all items are considered collectively, not individually, for each assessment and entry dates. For other parameters (e.g., laboratory tests, ECGs, vital signs, physical measurements), each parameter is considered individually.

b Target visit day and study days reflect 7-day offset that defines follow-up analysis period (see Section 7.1)

If there are multiple records collected or measured on the same day, then the last value entered is selected, unless specified otherwise in Section 7.4.

7.3 Derived Dates

Derived dates are obtained from full, valid numeric dates. Full dates are those that have non-missing day, month and year. Valid dates are those that are consistent with the calendar (e.g., "31FEB2017" is invalid). No imputation is performed, unless specified otherwise.

- Start date of study therapy is the earliest start date of any drug in the regimen (DCV or SOF) identified from full, valid numeric dates with total dose > 0 from study medication CRFs. This date is used to identify treated participants, define study and analysis periods, and assess time on study therapy. [This is the numeric version of SDTM DM.RFSTDTC, which is the same as DM.RFXSTDTC for this study.]
- End date of study therapy is the latest start or stop date of any drug in the regimen (i.e., DCV or SOF) identified from full, valid numeric dates with total dose > 0 from study medication CRFs. This date is used to assess time on study therapy. [This is the numeric version of SDTM DM.RFXENDTC.]
- Last date of study therapy is the end date of study therapy derived only for participants who completed or did not complete the treatment period based on the end of treatment subject status CRF. This date is used to define study and analysis periods, and assess time on study therapy. [This is the numeric version of SDTM DM.RFENDTC.]
- Last contact date is the death date, if it exists, or the latest of the following numeric dates: randomization; study therapy start or end; AE imputed onset or resolution; diagnostic procedure start; HCV RNA collection; laboratory test (safety, pregnancy) collection; last contact from end of treatment or end of study subject status; medical procedure start or stop; neurologic exam; vital signs; non-study medication imputed start or stop; palatability assessment; acceptability assessment; physical measurement; physical exam; viral genotype collection; vital phenotype collection.
- Start date of anti-HCV therapy on treatment or during follow-up is the earliest imputed concomitant or post-treatment numeric start date among anti-HCV medications (approved antiviral or immunomodulating agent; investigational antiviral or immunomodulating agent; see Section 7.4.5 and APPENDIX 1).

7.4 Domain-Specific Conventions

7.4.1 AEs

Missing and partial adverse event onset dates are imputed according to the AE Domain Requirements Specifications^{9,10} in place at the start of programming. Imputed dates are used to classify AEs into study and analysis periods. Counting rules for AEs, including those for exposure-adjusted multiple AEs, also follow these specifications.

7.4.2 Exposure

Derivations are based on study medication CRFs.

Start and end dates of individual study drugs (DCV and SOF) and formulations are derived analogously for participants with full, valid numeric dates with total dose > 0 (see Section 7.3).

The following conventions are applied to dosing calculations for each drug/formulation:

- Distinct records with non-missing numeric dose start date, total dose, and generic drug name are selected.
- Missing dose stop dates are imputed. The missing stop date of a dosing record is set to 1 day before the start date of the next available dosing record. If the participant started drug and was lost to follow-up (i.e., has only 1 record), the missing end date is set to the start date, thus crediting the participant with 1 day of dosing.
- Overlapping dose dates are modified. If the start date of a dosing record is equal to or before the end date of the previous dosing record, then the start date is set to 1 day after the previous end date.
- Total dose for a dosing record is calculated as the total dose recorded.
- Duration for a dosing record is calculated as stop date start date + 1.
- Total amount of drug taken is the sum of total dose x duration across dosing records.

Interruptions of individual study drugs (DCV and SOF) are identified from records with full, valid numeric start and stop dates, and total daily dose of 0. For participants who discontinued study therapy, only records with start dates before the last date of study therapy are selected, and end dates after the last date of study therapy are set to the last date of study therapy.

Dose adherence to a study drug (DCV or DOF) is defined as 100*minimum(average daily dose /target daily dose, 1):

- DCV: Target daily dose = 20 mg if Day 1 weight < 30 kg; 40 mg if 30 ≤ Day 1 weight < 45 kg; 60 mg if Day 1 weight ≥ 45 kg;
- SOF: Target daily dose = 400 mg for Cohort 1; TBD for Cohorts 2 and 3.

Day 1 weight is determined from IRT (see Section 6.3.2.3).

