7.4 Dosage Modification

Doses of DCV and SOF assigned on Day 1 cannot be modified but can be interrupted or discontinued to manage adverse events (See [Section 8.1](#)). In the event of interruption or discontinuation, both DCV and SOF must be stopped simultaneously. DCV+SOE treatment can be interrupted for a maximum of 7 days, and if not restored after 7 days, the treatment should be permanently discontinued.

Note: DCV dose modification will only be permissible if PK data from the initial 5 participants in a cohort suggest that the dose administered does not achieve the desired exposure criteria. The sponsor will advise how to modify the dose of DCV being administered, if needed.

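### A missing stop date on the last or only dosing record cuts a completer's derived treatment time short, because SAP 7.4.2 and 7.3 never check end of treatment status (minor)

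*SAP*

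**What the plan says.** SAP 7.4.2 introduces its imputation rules with "The following conventions are applied to dosing calculations for each drug/formulation". There are two rules for a missing stop date. If a later record exists, the stop is set to the day before that record starts. If the participant was lost to follow-up, the text continues: "i.e., has only 1 record), the missing end date is set to the start date, thus crediting the participant with 1 day of dosing". Duration is then given as "Duration for a dosing record is calculated as stop date start date + 1" (the minus sign between the two dates is lost in the text version). Start and end dates for each drug follow the same logic as the regimen-level dates in 7.3.

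In SAP 7.3 the end date of study therapy "is the latest start or stop date of any drug in the regimen", restricted to full, valid dates with a dose above zero. The general rule there is "No imputation is performed, unless specified otherwise". The last date of study therapy equals this end date, for participants whose end of treatment status shows that they completed or did not complete treatment. SAP 7.1 anchors the on-treatment and follow-up periods on that last date plus 7 days.

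On dosing, Protocol 7.4 states "Doses of DCV and SOF assigned on Day 1 cannot be modified", apart from interruption or discontinuation for adverse events and a sponsor-advised change after the PK review. Treatment is once daily for 12 weeks (Protocol 7.1).

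**The concern.** Having one dosing record is not the same as being lost to follow-up. Protocol 8.3 defines loss by failed contact attempts. With a fixed dose, an uninterrupted 12-week course needs no second record, so a completer could have a single record per drug. If its stop date is blank or partial, the plan credits one day even when the status CRF says that treatment was completed. The status CRF is already read in 7.3, but only to decide for whom a last date is derived, not what that date is.

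If records follow dispensing instead, a missing stop on the last of several records fits neither rule in 7.4.2: there is no next record, and it is not the only record. Its duration cannot be computed, and 7.3 falls back to the record's start.

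At stake are time on each drug and on study therapy (SAP 6.4.1), the split of adverse events and laboratory values between periods, the EOT HCV RNA value (SAP 6.5) and, under a narrower condition, the F/U WK 12 slot that defines SVR12.

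**Working it through.** **Inputs.** Full course: Day 1 to Day 84 (Protocol 7.1; Table 2-2 footnote a). Dispensing at Day 1, Day 10, Weeks 4 and 8 (Table 2-2). Follow-up windows F/U WK 4 [7, 49], F/U WK 12 [50, 119] and F/U WK 24 [120, 245], with a 7-day offset; the last HCV RNA collected in a follow-up window is used (SAP 7.2). Five participants enrolled (Protocol 10.1).

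**Formulas.** Duration = stop − start + 1. Follow-up day = study day − last date of study therapy − 7.

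**Plan's own figures.** One record with its stop set to its start: 1 − 1 + 1 = 1 day, as stated. Follow-up targets 7w − 7 for w = 4, 12, 24, 48, 72, 96, 108 give 21, 77, 161, 329, 497, 665, 749, which match Table 7.2-1.

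**Case A: one record per drug, one drug's stop missing.**
- That drug: 1 day (0.14 weeks) against 84 − 1 + 1 = 84 days (12.0 weeks).
- Mean over five: (4 × 12 + 1/7)/5 = 9.6 weeks, against 12.0.
- Last date of study therapy: still Day 84, from the other drug. The SVR12 window shifts by 0 days.

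**Case B: one record per dispensing interval, last stop missing.** Assume that the last record starts the day after the Week 8 visit, Day 57.
- One drug affected: its end date is Day 57, so 57/7 = 8.1 weeks; the regimen date is unchanged.
- Both drugs affected: last date = Day 57, and the on-treatment period ends on Day 57 + 7 = Day 64.

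**Case C: one record per drug, both stops missing.** The only full dates are the starts, so 7.3 gives last date = Day 1, a shift of 84 − 1 = 83 days. The on-treatment period ends on Day 8. F/U WK 12 covers study days 58 to 127 (50 + 7 + 1 to 119 + 7 + 1) instead of 141 to 210 (50 + 7 + 84 to 119 + 7 + 84).

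Slots at nominal visit days (number = follow-up day):

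| Sample (study day) | Last date 84 (true) | Last date 57 (B, both) | Last date 1 (C) |
|---|---|---|---|
| Day 10 (10) | on treatment | on treatment | 2, no window |
| Treatment Week 8 (56) | on treatment | on treatment | 48, F/U WK 4 |
| Treatment Week 12 (84) | on treatment | 20, F/U WK 4 | 76, F/U WK 12 |
| Post-Treatment Week 4 (112) | 21, F/U WK 4 | 48, F/U WK 4 | 104, F/U WK 12 |
| Post-Treatment Week 12 (168) | 77, F/U WK 12 | 104, F/U WK 12 | 160, F/U WK 24 |

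In case B with both stops missing, the Week 12 on-treatment sample moves to follow-up, so EOT is taken from Week 8. SVR12 still uses the right sample. A Post-Treatment Week 4 visit up to 7 days late (Day 119, follow-up day 55) would enter F/U WK 12, but the later Week 12 sample is the one selected. If the last record starts on Day 56, every follow-up day rises by one (21, 49, 105) and no slot changes.

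In case C, the Treatment Week 12 and Post-Treatment Week 4 samples share F/U WK 12. The later one is selected, so a Post-Treatment Week 4 result is labelled SVR12.

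**The case against.** The best defence is that 7.4.2 does mention loss to follow-up, and that a single record is sensible shorthand for it if completers have several. Drug is dispensed four times, and Protocol 7.6 requires dates and tablet counts at each visit, so several records per completer are quite possible. On that reading the 1-day rule never touches a completer. This has force as to intent, but it does not close the gap: a missing stop on the last record is then covered by no rule, and 7.3 still ends treatment at that record's start. If there is one record, the 7.3 logic gives the start date even without the 1-day sentence.

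A reader might infer that the 1-day rule moves the SVR12 window. The documents do not support that. The rule governs per-drug dosing calculations; the windows hang on the regimen date in 7.3, which is unaffected if either drug has a valid stop date.

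A reader might also infer inflated exposure-adjusted event rates or a false low-dose deviation. Neither can be sized. When the on-treatment period shrinks, later events leave the numerator as well as time leaving the denominator, and the SAP does not define the period over which average daily dose is taken.

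Practical reach is also limited, and this stands. Protocol 10.3.2 reports no virologic failure in any participant after at least 41 weeks of post-treatment follow-up. Protocol 10.3 plans no statistical analyses. CRFs are reviewed and signed by the investigator (Protocol Appendix 2), and nothing suggests that a stop date is missing.

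**Conclusion.** The point holds as a minor defect in the derivation rules. A documented completer with a missing stop on the last or only record is cut back to that record's start: 1 day instead of 84 with one record per drug, about 8.1 weeks instead of 12 with one record per dispensing interval. One single-record case moves the five-participant mean for that drug from 12.0 to 9.6 weeks.

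The effect on efficacy data is conditional. EOT HCV RNA is taken from too early a visit if both drugs' last stop dates are missing under per-dispensing records. SVR12 is mislabelled only with one record per drug and both stops missing, and then through 7.3 by itself. Since no participant had failed virologically, the SVR12 proportion would probably not change even then.

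This rests on assumptions that the documents cannot settle: the CRF layout, and whether any stop date is missing or partial. It remains worth correcting because Protocol 10.3 still reports SVR, adverse events, laboratory tests and end of treatment status. SVR and the period splits depend on these dates, and one participant is 20% of the sample.

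**What to change.** In SAP 7.4.2, apply the 1-day credit only when the end of treatment subject status records loss to follow-up and there is no later evidence of dosing. Otherwise, in both 7.4.2 and 7.3, set a missing stop on the last or only record to the last-dose date supported by the end of treatment status, the dosing diary or drug accountability. Use that same date for the last date of study therapy.

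Use the other drug's stop date only as a flagged fallback. The protocol's rule, "In the event of interruption or discontinuation, both DCV and SOF must be stopped simultaneously", covers interruption and discontinuation, not planned completion, so for a completer it is supporting evidence at most.

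The cost is about two sentences of SAP text and a small programming change. The diary and accountability data are already collected (Protocol 7.6). The downside is reliance on a secondary source for the imputed date, so such dates should be flagged in the listings.

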- Exclusion criterion 3c: Albumin < 35 g/L or < 3.5 g/dL
- Exclusion criterion 3d: Total bilirubin > 19 μmol/L or > 1.1 mg/dL without history of Gilbert syndrome. Gilbert syndrome is identified from general medical history specify details (#);
- Exclusion criterion 3e: Alpha fetoprotein > 50 ng/mL or > 50 µg/L
- Exclusion criterion 3f: ANC $< 1.5 \times 10^9$ cells/L or $< 1.5 \times 10^3$ cells/ μ L
- Exclusion criterion 3g: Hemoglobin < 100 g/L or < 10 g/dL
- Exclusion criterion 3h: Platelets < 100 x 10⁹ cells/L
- Exclusion criterion 3i: Creatinine clearance < 1 mL/s/m² or < 60 mL/min/1.73m², using the Schwartz formula.
- (#) Non-study medications and medical conditions marked above with # are identified by a BMS physician prior to database lock.

The screening portion of the pre-treatment analysis period begins at informed consent and ends before the start of study therapy (Day 1).

[figure not shown]
A participant with multiple pre-treatment measurements (e.g., HCV RNA) is considered to have an eligibility deviation only if all pre-treatment measurements meet the deviation criterion.

Participant Management Deviations

Participant management deviations are evaluated during the on-treatment or follow-up analysis period for the following categories:

- At least 2 consecutive missed doses of DCV before Day 10 PK sampling, or at least 1 missed dose of DCV within 2 days before Day 10 PK sampling. Missed doses of DCV are identified from interruptions or gaps between dosing records;
- At least twice of DCV target daily dose taken within 2 days before Day 10 PK sampling;
- DCV or SOF average daily dose < 80% of target daily dose;
- DCV or SOF interruption > 7 consecutive days;
- Continuation of study therapy after having virologic breakthrough;
- Use of prohibited non-study concomitant medication for more than 1 day, including anti-HCV medications (#). Generic drug names are presented alphabetically as subcategories;
- Use of non-study anti-HCV medication during follow-up (#). Generic drug names are presented alphabetically as subcategories;
- (#) Non-study medications marked above with # are identified by a BMS physician prior to database lock.

Anti-HCV Medications

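### The SAP 7.4.2 rule for overlapping dosing records gives a zero or negative duration to a record lying wholly inside a longer one, which can corrupt the < 80% average-daily-dose deviation

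*SAP*

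**What the plan says.** All the rules are in SAP 7.4.2 (Exposure), except the deviation itself.

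- **Selection:** "Distinct records with non-missing numeric dose start date, total dose, and generic drug name are selected". This removes identical rows, not records that conflict.
- **Overlap trigger:** a later record whose first day falls on or before the last day of the one preceding it. Full containment meets this condition as well as partial overlap.
- **Overlap action:** "then the start date is set to 1 day after the previous end date". No step truncates or splits the earlier record, or drops a later one that has no days left.
- **Duration:** "Duration for a dosing record is calculated as stop date start date + 1". The minus sign between the two dates was lost in text extraction; the meaning is stop minus start plus 1.
- **Amount:** "Total amount of drug taken is the sum of total dose x duration across dosing records".
- **Adherence:** average daily dose over target daily dose, capped at 100% with no lower bound. The divisor that turns an amount into an average daily dose is not given.
- **Target for DCV in Cohort 1:** "60 mg if Day 1 weight ≥ 45 kg".

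Interruptions are records with a daily dose of 0. SAP 6.4.2 summarises those longer than 3 consecutive days, and SAP Appendix 1 makes those longer than 7 consecutive days a relevant deviation. Appendix 1 also lists "DCV or SOF average daily dose < 80% of target daily dose" as a relevant deviation.

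**The concern.** The rule suits records that run in sequence and overlap at the edges. It does not suit a record contained in another. The contained record's start is pushed past its own stop, its duration goes to zero or below, and that duration is still multiplied by dose and summed.

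Two errors can follow, in opposite directions. An interruption entered as a 0 mg record inside a longer dosing record adds 0 mg, while the outer record still credits full dosing for the same days. A positive-dose record inside a longer one takes drug away from a participant who missed nothing. The amount feeds average daily dose and so the < 80% deviation. With five participants enrolled, one misclassification is 1/5 = 20% of the study.

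**Working it through.** The plan states no numerical result for this rule, so there is no figure to reproduce. The steps below apply SAP 7.4.2 literally to hypothetical DCV histories.

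**Inputs.** Course of 84 days (12 weeks; Protocol Table 2-2, footnote a, ends treatment on Day 84). Target 60 mg (SAP 7.4.2). Threshold 80% (SAP Appendix 1). Full amount = 84 × 60 = 5040 mg.

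**Algebra.** Let the outer record end on E1 and the nested record on E2 ≤ E1. The nested start becomes E1 + 1, so its duration is E2 − (E1 + 1) + 1 = E2 − E1. This is negative if E2 < E1 and 0 if E2 = E1. The nested record's own length does not enter.

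**Partial overlap, same dose.** Days 1-30 and 28-84: the second becomes 31-84, and 30 + 54 = 84 days. Correct.

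**Nested 0 mg records.** Outer record Days 1-84 at 60 mg.

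- Three nested interruptions of 6 days each: every one contributes 0 mg whatever its duration, so the amount stays 5040 mg. Over 84 days that is 60 mg/day = 100%. The true value is (84 − 18)/84 = 66/84 = 78.6%. The < 80% deviation is missed, and no interruption exceeds 7 days.
- One nested interruption, Days 30-46 (17 days): computed 100%, true 67/84 = 79.8%. With 16 days the true value is 68/84 = 81.0%, so 17 days is the shortest single interruption that falls below 80%, and it also exceeds 7 days.
- The same kind of gap entered as sequential records is handled correctly. Days 1-28 at 60 mg, 29-49 at 0 mg and 50-84 at 60 mg give 63 × 60 = 3780 mg, and 3780/5040 = 75.0%.
- If both records start on Day 1 and a 0 mg record for Days 1-21 sorts first, the outer record is moved to 22-84 (63 days), and the result is again 75.0%. The SAP gives no order for tied starts.

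**Nested positive-dose records.** Outer record Days 1-84 at 60 mg.

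- Nested Days 28-56 at 60 mg: the start becomes Day 85, and the duration is 56 − 85 + 1 = −28. Amount = 5040 − 28 × 60 = 3360 mg.

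| Denominator | Days | Average (mg/day) | % of target |
|---|---|---|---|
| Elapsed days | 84 | 40 | 66.7 (flagged) |
| Sum of durations | 84 − 28 = 56 | 60 | 100 (not flagged) |

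- On elapsed days the flag turns on the nested end date. Ending on Day 67 gives −17 days, 4020 mg and 79.8% (flagged). Ending on Day 68 gives −16 days, 4080 mg and 81.0% (not flagged). Ending on Day 84 gives 0 days and 100%.
- A nested record at a higher dose is flagged on either denominator. Day 10 at 120 mg has duration 10 − 84 = −74, so the amount is 5040 − 74 × 120 = −3840 mg. That is −45.7 mg/day over 84 days, or −384 mg/day over 84 − 74 = 10 days.

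**The case against.** The case for leaving the rule alone has five parts.

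1. *Nested records are hypothetical.* Stands. The documents show neither the dosing CRF nor its edit checks, and the missing-stop rule in SAP 7.4.2 suggests records expected in sequence. SAP 7 defers to sponsor conventions that are not available here, but only where the SAP does not specify otherwise, and 7.4.2 does specify.
2. *The false flag depends on an undefined denominator.* Stands for same-dose nesting. A reader might infer that a fully dosed participant with a nested same-dose record is bound to be flagged. The documents do not support that, since summed durations give 100%. The missed-interruption error does not need an elapsed-day denominator.
3. *Interruptions are caught elsewhere.* Partly stands. A reader might infer that a nested interruption is never deducted, or that an interrupted participant escapes notice. The first fails for the tied-start case. The second goes too far: a single interruption of 17 days or more also meets the > 7-day deviation, and the three 6-day gaps would appear in the > 3-day summary, if original dates are used. The SAP does not say whether they are. Even so, the three gaps would meet neither deviation category.
4. *Reach is narrow.* Stands. PK, SVR12, exposure-adjusted AE rates (SAP 6.6.2.2) and time on therapy (SAP 6.4.1) do not use this sum, and SAP 6.4 plans no summary of total dose or adherence.
5. *Little depends on it now.* Stands. The notes in Protocol 10.1 and 10.3 record five participants and no statistical analyses, and adherence is not named among the data to be reported. Five dosing histories can be checked by hand.

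**Conclusion.** The point holds as a defect in a stated rule, not as a missing detail: applied as written, SAP 7.4.2 gives a wholly contained record a duration of E2 − E1.

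For a nested 0 mg record that starts after the outer one, the interruption is lost from the amount taken; the worked size is 100% computed against 78.6% true. For a nested positive-dose record at the same dose, the result is 66.7% or 100% for someone fully dosed, depending on a denominator the SAP does not define.

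These figures assume an 84-day course at 60 mg and that nested records occur in the data, which the documents do not show. The planned output affected is the < 80% average-daily-dose deviation in Appendix 1. Given that reach and five participants, this is a nice-to-have correction and does not threaten the trial's main results.

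**What to change.** Amend SAP 7.4.2 as follows.

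- Compute the amount taken by calendar day, counting each day once for each drug. A record with no days left after overlaps are resolved contributes nothing, and durations are floored at 0.
- Define average daily dose as the amount taken divided by the days from first to last dose of that drug.
- Identify interruptions, for both the > 3-day summary and the > 7-day deviation, from original, unshifted dates.
- Query every nested or conflicting record before database lock, whether 0 mg against a positive dose or two differing positive doses. The 0 mg entry may itself be the error, so the query comes first.
- For conflicts left unresolved, state one default for each type. For example, a 0 mg record splits the record around it; where two positive doses differ, name the record whose dose is used in the calculation.

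The cost is SAP wording and a minor program change, with no new data collection.
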